#### 3.1.1 Primary objective

The primary objective of this proposed study is to compare the magnitude of the responses to a 6-month cardiac rehabilitation program for patients with PAD in contrast to patients with CAD. The primary variable of interest will be peak oxygen consumption ( $VO_2\text{peak}$ ) with a secondary variable of interest being functional capacity, as measured by the 6-minute walk test. Tertiary variables of interest will include walking impairment, as measured by the Walking Impairment Questionnaire, and quality of life, as measured by the Short Form-36 health survey (SF-36).

#### 3.1.2 Secondary objectives

The second objective of this proposed study is to determine if the magnitude of responses to cardiac rehabilitation for patients with PAD are dependent on biological sex or type of PAD (asymptomatic, post-surgical intervention, or intermittent claudication).

#### 3.1.3 Exploratory objectives

The exploratory objective is to compare acute exercise responses (prescribed exercise training load, actual training load, exercising heart rate and rating of perceived exertion) between PAD and CAD patients.

#### 3.2 Study hypothesis

The primary hypothesis is that patients with CAD will have greater improvements in  $VO_2\text{peak}$  and 6-minute walk test compared to patients with PAD (Lucini et al., 2002; Parmenter, et al., 2015). However, considering the walking limitations patients with PAD often have and the improvements observed with exercise training (Milani & Lavie, 2007; Novakovic et al., 2016), it is hypothesized that patients with PAD will have greater improvements in the WIQ and QOL compared with patients with CAD. Furthermore, a secondary hypothesis that the magnitude of response for patients with PAD will be dependent on biological sex and type of PAD. Lastly, it is hypothesized that patients with PAD on average will have a greater exercising heart rate, rating of perceived exertion and rating of pain severity compare to patients with CAD.

## **4.0 Study Design**

### **4.1 Primary and secondary endpoints**

Patients will undergo a baseline assessment with a laboratory technician involving a standard battery of measurements and questionnaires for characteristic purposes including anthropometrics, resting blood pressure, resting heart rate, smoking status, diabetes status, current exercise regimen, and current medications. During this assessment, clinicians will review previous and ongoing medical treatment (i.e. surgical procedures, next physician visit, ankle-brachial index measurement), presence of angina, and conduct resting 12-lead electrocardiograms. This will be followed by a medical assessment by a physician to further review medical history and safety precautions for exercise. Patients will be sent home with a walking impairment questionnaire (WIQ) (McDermott et al., 1998) and a quality of life (QOL) questionnaire (SF-36) (Brazier et al., 1992) to be submitted at their next visit. A requisition for blood work will also be given to patients to be completed prior to their second visit to determine HbA1c and total cholesterol levels.

During the second visit patients will undergo a maximal cardiopulmonary exercise test to determine cardiorespiratory fitness as measured by VO2peak and will also have an exercising 12-lead electrocardiogram. The cardiopulmonary exercise test will consist of a Bruce or modified Bruce treadmill protocol (Noonan and Dean, 2000).

After determining baseline VO2peak, an individualized walking exercise prescription will be developed by a cardiac rehabilitation supervisor which corresponds to approximately 60 to 80% of VO2peak. Patients will be invited to attend weekly 90-minute supervised exercise and education sessions at the same time every week for six months, as per standard care procedures. Patients will be encouraged to gradually increase their exercise time per session as well as frequency of sessions per week.

Clinicians at TRI will record distance walked, rest periods, exercising heart rate (as palpated by the radial pulse), ratings of perceived exertion and ratings of pain severity on a scale of 0 (no pain) to 10 (worst imaginable pain) (Hawker, Mian, Kendzerska, & French, 2011) for each exercise session at TRI. Patients will self-record their other exercise sessions on a weekly basis using standard exercise diaries. Frequency, time, type, exercising heart rate and rating of perceived exertion will be recorded for each exercise session outside of TRI. Patients will wear a non-invasive heart rate monitor (Polar) while walking at the 2nd week, 3rd month and 6th month mark of the program to help determine acute responses to aerobic exercise. Average exercising heart rate will be measured and recorded. VO2peak, 6MWT, QOL (SF-36), and walking impairment (WIQ) will be re-assessed at the 3 month and 6 month mark of the program.

Training volume will be quantified for each group for the prescribed and actual exercise load. For aerobic exercise, training will be calculated as the product of intensity in heart rate reserve, duration, and frequency for both the prescribed and actual exercise. For resistance exercise, training will be calculated as the product of weight, numbers of sets, and number of repetitions for each exercise for both prescribed and actual exercise.

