## Comparing the efficacy of cardiac rehabilitation for patients with peripheral artery disease to patients with coronary artery disease/Protocol #03

The primary endpoints of interest include change in VO2peak from month 6 to baseline, change in 6 minute walk test distance from month 6 to baseline, as well as change in walking impairment and quality of life as assessed through questionnaires from month 6 to baseline.

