### 5.3 Withdrawal of Subjects

Participants may choose to withdraw from the study at any time. Any data collected will be discarded immediately.

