## **8.0 Statistics**

### **8.1 A description of the statistical methods to be employed**

Primary analysis to determine if patients with CAD or patients with PAD have greater improvements in  $VO_2$ peak, 6MWT, WIQ, and QOL will be tested with a series of two factor 2 (time: Baseline, End) by 2 (group: PAD, CAD) analyses of variances with Tukey's Honest Significant Difference (HSD) test for post-hoc corrections. This analysis will include patients who attended  $>70\%$  of on-site cardiac rehabilitation sessions. An intention-to-treat analysis will be conducted to include patients who attended less than 70% of the cardiac rehabilitation program sessions.

The secondary hypothesis that the magnitude of responses for patients with PAD will be dependent on biological sex will be tested through conducting a 3 factor 2 (time: Baseline, End) by 2 (group: PAD, CAD) by 2 (sex: men, women) analysis of variance. In addition to determine if the magnitude of responses are dependent on clinical presentation of PAD, a 2 factor 2 (time: Baseline, End) by 2 (type: asymptomatic, post-surgical intervention, IC) analysis of variance will be conducted.

To determine if PAD patients have greater exercising heart rate, rating of perceived exertion (Borg scale), rating of pain severity (, and training volumes than CAD patients, tertiary analysis will involve independent t-tests for these variables.

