### **8.2 The number of subjects planned to be enrolled**

Sample size calculations were conducted using an alpha of 5% and a power of 0.8. Calculations were based on the primary and secondary variables of interest ( $VO_2$ peak

Comparing the efficacy of cardiac rehabilitation for patients with peripheral artery disease to patients with coronary artery disease/Protocol #03

and 6MWT distance) for PAD and CAD patients. To be conservative, the largest sample size (6MWT) was selected.

Previous literature has found that patients with PAD undergoing exercise training compared to PAD patients who did not undergo exercise training had improvements in the 6MWT of 34.9m (95 % CI 25.6–44.1 m,  $P<0.00001$ ) (Parmenter et al., 2015). In contrast, patients with CAD had improvements of  $29.6\pm12$ m following exercise training (Jaureguizar et al., 2016). Clinically significant changes have been defined as 20m for the 6MWT (Perera et al., 2006). A difference of 10 meters between groups is a conservative average between what is observed in the literature and the defined clinically significant change. The sample size calculation for a power of 0.8 would be 23 participants per group. Accounting for a 20% drop out, 28 patients with CAD and 28 patients with PAD will be recruited. Statistical significance will be set at a  $P$  value of 0.05.

A sample size of 28 participants per group is powered to detect a difference of 1.6 ml/kg/min between groups for VO2peak.

8.3 Procedure for accounting for missing, unused, and spurious data.

If data variables are missing, the whole participant data set will be excluded from the main statistical analysis. If some data is available, the participant's data will be included in the intention to treat analysis.

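### The month-3 outcome data go unused and one missing variable removes a whole participant from the main analysis; outcome-by-outcome inclusion with a repeated-measures model is a cheap, modest improvement

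*Combined protocol and SAP*

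**What the plan says.** Section 4.1 plans three measurements of each main outcome: after baseline, VO2peak, 6MWT, SF-36 and WIQ "will be re-assessed at the 3 month and 6 month mark of the program". The endpoints in the same section are changes between baseline and month 6, for example "change in 6 minute walk test distance from month 6 to baseline".

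Section 8.1 specifies the primary analysis as a series of "two factor 2 (time: Baseline, End) by 2 (group: PAD, CAD) analyses of variances". "This analysis will include patients who attended" more than 70% of on-site sessions, it says; those below 70% enter an intention-to-treat analysis. No analysis in section 8 uses the month-3 values of the four outcomes.

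Section 8.3 has two rules. For the main analysis: "If data variables are missing, the whole participant data set will be excluded from the main statistical analysis". For the other: "If some data is available, the participant's data will be included in the intention to treat analysis". It names no model or imputation method for that second analysis.

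Two further places bear on the point. Section 5.3 says of participants who withdraw: "Any data collected will be discarded immediately". The visit schedule in section 4.6 names the exercise test only at visit 2. It lists the 6MWT and questionnaires at visits 5 and 6, but no VO2peak test at either.

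**The concern.** The four outcomes are analysed separately, yet section 8.3 ties them together. Taken literally, a patient with VO2peak at baseline and month 6 who does not return an SF-36 or WIQ leaves the main VO2peak analysis. That is a realistic loss, because section 4.6 has the baseline and visit-5 questionnaires completed between visits. The plan gives no reason for it.

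A patient measured at baseline and month 3 but not at month 6 cannot enter a Baseline/End ANOVA, whichever analysis set is used. The month-3 value is the natural predictor of the missing month-6 value, and it is set aside.

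Two things are at stake. The first is precision, in a study of 28 per group with almost no margin over 80% power. The second is bias in the comparison of peripheral artery disease (PAD) with coronary artery disease (CAD), should loss depend on response and differ between the groups. Section 3.2 expects more pain in PAD, and section 7.0 notes that patients with claudication often exercise to pain tolerance. Unequal loss is therefore plausible, though the documents do not establish it.

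**Working it through.** **The plan's own figure.** Inputs from section 8.2: difference 10 m, alpha 5%, power 0.8, and SD 12 m (the only SD given there, from the cited CAD study). Two-sided, n per group = 2 × (1.960 + 0.842)² × 12² / 10² = 22.6, rounded up to 23. This matches. The planned 28 is 23 × 1.2 = 27.6, rounded up.

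**Complete cases at the planned 20% loss.** 28 × 0.8 = 22.4 per group. SE = 12 × √(2/22.4) = 3.59 m, and power for 10 m is 0.796.

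**Adding month 3.** Let p = 0.8 be the share with month 6, g the share of the remainder with month-3 data, and r the correlation between the month-3 and month-6 changes. The documents give neither g nor r; both are assumptions. In large samples, with loss unrelated to response, the effective n per group under maximum likelihood is 28 / [(1 − r²)/p + r²/(p + (1 − p)g)].

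| r | g | effective n per group | SE (m) | power |
|---|---|---|---|---|
| 0.3 | 0.5 | 22.6 | 3.57 | 0.800 |
| 0.5 | 0.5 | 23.0 | 3.54 | 0.807 |
| 0.5 | 1 | 23.6 | 3.49 | 0.816 |
| 0.8 | 0.5 | 24.1 | 3.46 | 0.825 |
| 0.8 | 1 | 25.7 | 3.35 | 0.848 |

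Top row: 0.91/0.8 + 0.09/0.9 = 1.2375, and 28/1.2375 = 22.6. Bottom row: 0.36/0.8 + 0.64/1 = 1.09, and 28/1.09 = 25.7. The variance reduction runs from 1% to 13%.

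**Bias.** Simulation: 28 per group, 4,000 replicates, true difference 10 m, SD 12 m, all lost patients having month-3 data (g = 1), and poorer month-3 response raising the chance of loss. Loss was about 30% in the group with the smaller improvement and 10% in the other.

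| r | bias, complete cases (m) | bias, with month 3 (m) | SE, complete cases | SE, with month 3 |
|---|---|---|---|---|
| 0.3 | −0.61 | −0.07 | 3.66 | 3.83 |
| 0.5 | −0.96 | 0.00 | 3.71 | 3.79 |
| 0.7 | −1.33 | 0.01 | 3.58 | 3.56 |
| 0.8 | −1.49 | 0.00 | 3.50 | 3.42 |

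With about 20% loss in both groups, bias was within about 0.1 m of zero either way. When loss depends on response, the month-3 estimate (here from a separate regression in each group) removes the bias but is not more precise at low r.

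**The section 8.3 rule.** Assume each of the four outcomes is independently missing at month 6 in 5% of patients. Then 0.95⁴ = 0.81 of patients are complete, or 28 × 0.8145 = 22.8 per group. Deciding outcome by outcome keeps 28 × 0.95 = 26.6 for each. Both counts are before any attendance exclusion.

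**The case against.** A two-level model is not an error. The endpoint is the change from baseline to month 6, and the time-by-group interaction of a 2 × 2 ANOVA tests exactly that. If every patient is complete at all visits, an unstructured repeated-measures model gives essentially the same month-6 contrast. This stands: the gain comes only from patients with a missing End value.

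The gain is also limited by other rules. Data of participants who withdraw are discarded under section 5.3, so g is 0 for them. The attendance restriction keeps many early stoppers out of the main analysis. Taking six months as 26 weekly sessions, a patient who stops at month 3 has attended at most about 13, or 50%. (Sections 2.4 and 5.2 also express the cut-off as fewer than 10 sessions, which such a patient could meet; 70% of 26 is 18.2.) For VO2peak, the primary variable, sections 4.1 and 4.6 disagree on whether a month-3 test takes place. These limits stand too, and the improvement is not wholly free.

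Three stronger readings are tempting and are not supported.
- A reader might infer that a patient with one missing questionnaire contributes nothing to any VO2peak result. Section 8.3 admits such patients to the intention-to-treat analysis. What is missing is a method there for a patient without an End value.
- A reader might count eight follow-up measurements (four outcomes at two times) and conclude that 5% missingness leaves 0.95⁸ = 66%. The main model uses no month-3 value, so the four month-6 outcomes, giving 81%, are the better count. Even that assumes independence; a missed visit loses several outcomes together and would leave more patients complete.
- A reader might conclude that the main comparison will be biased. The documents give no loss by group and no cause of loss, and equal loss produced almost no bias.

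**Conclusion.** The concern holds as a cheap improvement. Two parts are firm on the text alone: whole-participant deletion links outcomes that are analysed separately, and the intention-to-treat analysis has no stated way to use a patient without an End value. Using month 3 is a better method of modest benefit. At 20% loss it moves an effective 22.4 per group to between 22.6 and 25.7, and power from 0.796 to between 0.800 and 0.848, for r of 0.3 to 0.8 and g of 0.5 to 1.

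Protection against bias is conditional. It needs loss that differs between the groups and is missing at random given the observed data. In the simulated case it is worth 0.6 to 1.5 m on a 10 m difference. The figures r, g, the 5% missingness and the 30% versus 10% loss are all assumptions, and for VO2peak everything depends on the month-3 test actually being done.

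**What to change.** 1. In section 8.3, delete the whole-participant exclusion and decide inclusion separately for each outcome.
2. In section 8.1, replace the 2 × 2 ANOVA with a mixed model for repeated measures on baseline, month 3 and month 6: group, time, group × time, unstructured covariance. The test is the group contrast in change at month 6, so the endpoint is unchanged. Leave the baseline means free in each group, since the groups are not randomised.
3. Name the same model for the intention-to-treat analysis, so that patients with month-3 but no month-6 data contribute, and state the missing-at-random assumption.
4. Reconcile three places with this: the discarding of withdrawn participants' data (section 5.3); the attendance restriction on the main analysis (sections 2.4, 5.2 and 8.1), including which analysis set each contrast uses; and the timing of VO2peak tests in section 4.1 against the visit schedule in section 4.6.

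The cost is revised wording, slightly more analysis work and reliance on missing at random. No measurement is needed beyond those section 4.1 already plans, but if the schedule in section 4.6 is what is followed, month-3 VO2peak will not exist and step 2 helps only the 6MWT and the questionnaires.

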## Comparing the efficacy of cardiac rehabilitation for patients with peripheral artery disease to patients with coronary artery disease/Protocol #03

The primary endpoints of interest include change in VO2peak from month 6 to baseline, change in 6 minute walk test distance from month 6 to baseline, as well as change in walking impairment and quality of life as assessed through questionnaires from month 6 to baseline.

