### **Primary Objective**

The primary objective of this proposed study is to compare the magnitude of the responses to a 6-month cardiac rehabilitation program for patients with PAD in contrast to patients with CAD. The primary variable of interest will be peak oxygen consumption (VO2peak) with a secondary variable of interest being functional capacity, as measured by the 6-minute walk test. Tertiary variables of interest will include walking impairment, as measured by the Walking Impairment Questionnaire, and quality of life, as measured by the Short Form-36 health survey (SF-36).

**Secondary Objective** The second objective of this proposed study is to determine if the magnitude of responses to cardiac rehabilitation for patients with PAD are dependent on biological sex or type of PAD (asymptomatic, post-surgical intervention, or intermittent claudication).

**Exploratory Objectives** Exploratory objectives include comparing acute exercise responses (prescribed exercise training load, actual training load, exercising heart rate and rating of perceived exertion) between PAD and CAD patients.

**Endpoints of the study** This study will allow for the comparison of the efficacy of cardiac rehabilitation for CAD and PAD patients to provide further support of the application of exercise rehabilitation for PAD patients. In addition, this study will inform future studies investigating optimal exercise prescriptions for PAD patients.

Comparing the efficacy of cardiac rehabilitation for patients with peripheral artery disease to patients with coronary artery disease/Protocol #03

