## **7.0 Assessment of Efficacy**

Peak oxygen consumption (VO2peak) measured through a treadmill test is a standard measure of cardiorespiratory fitness. A meta-regression analysis of various treadmill protocols for patients with PAD found that continuous protocols had an intraclass correlation coefficient (ICC) of 0.85 (95% CI 0.82 to 0.88) and graded protocols had an ICC of 0.83 (95% CI 0.80 to 0.85). Graded protocols were more reliable than continuous protocols for absolute claudication distance (ICC=0.95, 95% CI 0.94 to 0.96). Continuous protocols had the greatest reliability at a grade of 12 % (ICC=0.91, 95% CI 0.88 to 0.92) (Nicolai et al., 2009). In addition to being used for characteristic purposes, VO2peak can also be an outcome measure to determine the effectiveness of interventions. In a systematic review and meta-analysis, the mean difference in relative VO2peak for PAD patients who underwent exercise training compared to control patients was 0.62 ml/kg/min (95%CI 0.47 to 0.77, P<0.00001) (Parmenter et al., 2015). This suggests that VO2peak is responsive to changes following exercise interventions. It should be noted that although VO2peak is one parameter used to define intensity in exercise prescriptions, PAD patients with IC often exercise according to pain tolerance (Hamburg & Balady, 2011).

The walking impairment questionnaire (WIQ) is a validated method of quickly measuring walking ability in men and women with PAD (McDermott et al., 1998). The WIQ consists of 14 items related to walking distance, walking speed and stair climbing ability using a scale from 0 to 4 to rank degree of difficulty. An overall score below 42.5 suggests a patient with low walking ability (sensitivity 0.90, specificity of 0.73) whereas a score above 75.5 suggests a patient with a high walking ability (sensitivity 0.41, specificity 0.90) (Sagar, Brown, Zelt, Pickett & Tranmer, 2012). In a cross-sectional

Comparing the efficacy of cardiac rehabilitation for patients with peripheral artery disease to patients with coronary artery disease/Protocol #03

study validating the WIQ, the WIQ distance score was moderately correlated with 6MWT times with a Spearman rank correlation coefficient of 0.557 for patients with PAD (McDermott et al., 1998). Considering the evidence, the WIQ is a useful clinical tool to assess walking ability.

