Montgomery and Gardner (1998) determined test-retest reliability using multiple 6MWT trials among 64 PAD patients. The distance walked and number of steps taken were similar between trials with a reliability coefficient of  $R=0.94$  and  $R=0.90$ , respectively. QOL can be measured through standardized general questionnaires such as the Short-Form 36 health survey (SF-36). The SF-36 is the most common instrument used to measure health related QOL in physical activity research (Hart & Kang, 2015; Novakovic et al., 2016; Stoner et al., 2016). It has high internal consistency (Cronbach's  $\alpha>0.8$ ), with the exception of social functioning likely due to having only two items in that domain ( $\alpha=0.79$ ), among older adults (Brazier et al., 1992; Walters, Munro & Brazier, 2001). A meta-analysis of the reliability of the SF-36 in physical activity research with various research designs and patient populations found strong effect sizes (ES) for physical health ( $ES=0.90$ , 95% CI: 0.88 to 0.92,  $P<0.001$ ) and mental health ( $ES=0.90$ , 95% CI: 0.89 to 0.91,  $P<0.001$ ) domains (Hart & Kang, 2015). This suggests that the SF-36 is a responsive measure of QOL for physical activity research. The SF-36 is also considered to be a suitable general measure of QOL for patients with PAD (Mehta, Subramaniam & McCollum, 2003).

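### The protocol gives three versions of what is primary, and section 8.1 does not tie the primary claim to VO2peak or to the time-by-group effect

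*Combined protocol and SAP*

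**What the plan says.** The current text holds three versions.

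- **Ranked (Protocol Summary and 3.1.1).** Section 3.1.1 says "The primary variable of interest will be peak oxygen consumption". The Summary and 3.1.1 then continue "with a secondary variable of interest being functional capacity, as measured by the 6-minute walk test". The third tier is "Tertiary variables of interest will include walking impairment, as measured by the Walking Impairment Questionnaire, and quality of life". Section 8.2 keeps the first two ranks when it describes the sample size.
- **Unranked (4.1).** The list opens "The primary endpoints of interest include change in" VO2peak, adds the 6-minute walk distance, and ends "as well as change in walking impairment and quality of life as assessed through questionnaires from month 6 to baseline". The subsection is headed as covering primary and secondary endpoints, but it labels none of them secondary.
- **Paired (3.2).** The primary hypothesis covers VO2peak and 6MWT together, both expected to favour CAD. For the questionnaires the expected direction is reversed: "it is hypothesized that patients with PAD will have greater improvements in the WIQ and QOL compared with patients with CAD".

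Section 8.1 places all four outcomes under its primary analysis, each in its own 2 (time) by 2 (group) analysis of variance, with Tukey's HSD as the post-hoc correction. Section 8.2 sets significance at P 0.05, with no split and no order of testing.

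**The concern.** The study's headline depends on which section the reader opens. Under 3.1.1 only VO2peak can carry the primary claim. Under 4.1 any of four outcomes might. Under 3.2 it is VO2peak and 6MWT, without saying whether one or both must succeed.

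This matters more than usual because 3.2 expects opposite directions. A mixed picture, with CAD ahead on fitness and walking distance and PAD ahead on the questionnaires, is what the investigators predict. Under 4.1 either half of that picture could be presented as the primary finding.

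Section 8.1 does not settle it. A 2 by 2 analysis of variance yields a time effect, a group effect and a time-by-group effect. Only the last compares improvement between groups, and 8.1 does not name it as the deciding test.

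**Working it through.** **1. The labels side by side.**

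| Outcome | Summary, 3.1.1 | 8.2 | 3.2 | 4.1 | 8.1 |
|---|---|---|---|---|---|
| VO2peak | primary | primary | primary hypothesis | primary | primary analysis |
| 6MWT | secondary | secondary | primary hypothesis | primary | primary analysis |
| WIQ | tertiary | not ranked | separate hypothesis | primary | primary analysis |
| SF-36 | tertiary | not ranked | separate hypothesis | primary | primary analysis |

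Section 8.1 also uses the word tertiary for the acute-response t-tests, whereas 3.1.1 uses it for WIQ and SF-36.

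**2. The plan's own sample size.** Inputs from 8.2 are a 10 m difference, 5% alpha and 80% power. I take the SD as 12 m, from the CAD figure quoted there, and the test as two-sided. Both are assumptions, supported by the match:

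n = 2 × (1.960 + 0.842)² × 12² / 10² = 22.6, so 23 per group; 23 × 1.2 = 27.6, so 28.

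This reproduces the stated figures. It is the size for one test at 0.05, with no allowance for several primary endpoints.

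**3. What the labels could mean for the false-positive rate.** This is an illustration. I assume no true group difference on any outcome and four normal test statistics with a common correlation r. The documents give no correlations, so I use 0 to 0.7. The critical value is 1.96. At r = 0:

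- any one of four, two-sided: 1 − 0.95⁴ = 0.185;
- any one of four, counting only the directions in 3.2: 1 − 0.975⁴ = 0.096;
- all four required: 0.05⁴ = 0.000006.

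For r above 0 the probabilities come from numerical integration over the shared component.

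| Rule | r = 0 | 0.3 | 0.5 | 0.7 |
|---|---|---|---|---|
| VO2peak only | 5% | 5% | 5% | 5% |
| Any of four, two-sided | 18.5% | 17.4% | 15.6% | 13.0% |
| Any of four, 3.2 directions only | 9.6% | 9.5% | 9.1% | 8.3% |
| All four, two-sided | <0.01% | 0.02% | 0.15% | 0.58% |

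**4. Tukey's HSD.** It adjusts comparisons among the means of one outcome within one analysis of variance. It does not change any row of this table.

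**5. What 8.2 supports for VO2peak as sole primary.** Section 8.2 gives a detectable difference of 1.6 ml/kg/min at 28 per group, with no SD. I assume this means 80% power in a two-sided 0.05 t-test. The detectable standardised difference at 28 per group is then 0.762, so the implied SD is 1.6 / 0.762 = 2.10. At 23 per group the power for 1.6 falls to about 72%, and the difference detectable with 80% power rises to about 1.77.

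**The case against.** The best defence is that primary means belonging to the primary objective. Section 3.1.1 places all four outcomes under that objective and ranks them inside it. Section 8.1 then follows the order of section 3.1: the primary analysis covers the four outcomes of 3.1.1, the next paragraph covers 3.1.2, and the tertiary analysis covers the acute responses of 3.1.3. On that view 8.1 numbers objectives, 3.1.1 numbers variables, and 4.1 is loosely worded. This is plausible for 8.1 and may be what was meant in 4.1. It does not remove the conflict, because 4.1 attaches the label to the endpoints themselves and says nothing of rank. Nor does it explain why 3.2 puts 6MWT in the primary hypothesis.

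Three stronger readings are tempting, and the documents do not support them.

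- *That no primary variable is named.* The Summary and 3.1.1 name VO2peak, and 8.2 relies on it. What is missing is the sentence that joins that ranking to a test in 8.1.
- *That the study has an 18.5% error rate.* Each test keeps its 5%. The higher figure needs a rule that any one success suffices, and the plan neither states nor excludes such a rule. The separate directional hypotheses in 3.2 fit it poorly.
- *That questionnaire subscores multiply the tests further.* Section 7.0 says "The WIQ consists of 14 items related to walking distance, walking speed and stair climbing ability", but it also interprets an overall score. Its remark that a meta-analysis "found strong effect sizes (ES) for physical health" and mental health is background on the instrument. Section 8.1 does not propose testing subscores.

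**Conclusion.** The point stands as a contradiction in current text, with high confidence. Section 4.1 conflicts with 3.1.1, 3.2 agrees with neither, and 8.1 leaves the deciding outcome and effect unnamed. As 4.1 is worded, an outcome ranked tertiary in 3.1.1 could be reported as a primary finding.

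Confidence in the numerical consequence is lower. The range runs from no inflation to 18.5%, depending on an unstated success rule and on assumed correlations, so it shows what the ambiguity could allow and does not estimate this study's error rate. The ranking that the investigators appear to intend is already in the document, so this is a correction that should be made, not a flaw in the design.

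**What to change.** - **4.1.** Replace the list with: *The primary endpoint is change in VO2peak from baseline to month 6. Change in 6MWT distance is secondary; changes in WIQ and SF-36 are tertiary.*
- **3.2.** Restrict the primary hypothesis to VO2peak and give the 6MWT, WIQ and quality-of-life hypotheses the same ranks. This edit is needed: otherwise 6MWT would be secondary in 4.1 and still part of the primary hypothesis.
- **8.1.** Name the time-by-group test for VO2peak, two-sided at 0.05, as the sole primary test. Report the group differences in change for the other three outcomes with 95% confidence intervals, as supportive.
- **8.2.** Show the VO2peak calculation with its SD and restate the detectable difference for the 23 evaluable per group.

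The cost is wording, with no new data or patients. The sponsor gives up presenting a lone 6MWT, WIQ or SF-36 result as primary. Section 8.2 says the larger, 6MWT-based sample size was adopted, so the planned number need not rise on its account. That rests on a VO2peak calculation that is not shown, hence the 8.2 edit.

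Keeping four primary endpoints with any one sufficient would cost more. Under Bonferroni each test runs at 0.05 / 4 = 0.0125, and the 6MWT case needs 2 × (2.498 + 0.842)² × 12² / 10² = 32.1, so 33 evaluable per group. That means 40 recruited with the plan's 1.2 multiplier, or 42 if 33 is divided by 0.8, against 28 planned.
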